8.2.2 DEFINITION OF SERIOUS ADVERSE EVENTS

A serious adverse event (SAE) will be considered any undesirable sign, symptom, or medical condition which is fatal, is life-threatening, requires or prolongs inpatient hospitalization, results in persistent or significant disability/incapacity, constitutes a congenital anomaly or birth defect, is medically significant and which the investigator regards as serious based on appropriate medical judgment. An important medical event is any AE that may not result in death, be life-threatening, or require hospitalization but may be considered an SAE when, based upon appropriate medical judgment, it may jeopardize the patient and may require medical or surgical intervention to prevent one of the outcomes listed in the definitions of SAEs.

8.2.3 CLASSIFICATION OF AN ADVERSE EVENT

8.2.3.1 SEVERITY OF EVENT

The following guidelines will be used to describe AE severity.

- **Mild** – Events require minimal or no treatment and do not interfere with the participant's daily activities.
- **Moderate** – Events result in a low level of inconvenience or concern with the therapeutic measures. Moderate events may cause some interference with functioning.
- **Severe** – Events interrupt a participant's usual daily activity and may require systemic drug therapy or other treatment. Severe events are usually potentially life-threatening or incapacitating. Of note, the term "severe" does not necessarily equate to "serious".

8.2.3.2 RELATIONSHIP TO STUDY INTERVENTION

All AEs will have their relationship to study procedures, including the intervention, assessed by the PI based on temporal relationship and his clinical judgment. The degree of certainty about causality will be graded using the categories below.

- **Definitely Related** – There is clear evidence to suggest a causal relationship, and other possible contributing factors can be ruled out. The clinical event, including an abnormal laboratory test result, occurs in a plausible time relationship to study procedures administration and cannot be explained by concurrent disease or other drugs or chemicals. The response to withdrawal of the study procedures should be clinically plausible. The event must be pharmacologically or phenomenologically definitive.
- **Probably Related** – There is evidence to suggest a causal relationship, and the influence of other factors is unlikely. The clinical event, including an abnormal laboratory test result, occurs within a reasonable time after administration of the study procedures, is unlikely to be attributed to concurrent disease or other drugs or chemicals, and follows a clinically reasonable response on withdrawal.
- **Possibly Related** – There is some evidence to suggest a causal relationship (e.g., the event occurred within a reasonable time after administration of study procedures). However, other factors may have contributed to the event (e.g., the participant's clinical condition, other concomitant events). Although an AE may rate only as "possibly related" soon after discovery, it can be flagged as requiring more information and later be upgraded to "probably related" or "definitely related", as appropriate.

8.2.3.3 TIME PERIOD AND FREQUENCY FOR EVENT ASSESSMENT AND FOLLOW-UP

Recording/reporting of AEs will begin after the subject signs informed consent and end after the subject completes the intervention and follow up period as defined in the protocol.

8.2.3.4 ADVERSE EVENT REPORTING

All AEs, as defined above, will be collected and reported. Data collection will occur via electronic spreadsheet. The information will be saved in REDCap and managed by the study team. In consultation with the PI, a trained member of the study team will be responsible for conducting an evaluation of a SAE and shall report the results of such evaluation to the NIH and the reviewing Institutional Review Board (IRB) as soon as possible and in accordance with the reviewing IRB policy

8.2.3.5 SERIOUS ADVERSE EVENT REPORTING

In consultation with the PI, a trained member of the study team will be responsible for conducting an evaluation of a SAE and shall report the results of such evaluation to the NIH and the reviewing IRB as soon as possible and in accordance with the reviewing IRB policy.

8.2.3.6 REPORTING EVENTS TO PARTICIPANT

N/A

8.2.3.7 EVENTS OF SPECIAL INTEREST

N/A

8.2.3.8 REPORTING OF PREGNANCY

N/A

8.3 UNANTICIPATED PROBLEMS

8.3.1 DEFINITION OF UNANTICIPATED PROBLEMS

This protocol uses the definition of Unanticipated Problems (UP) as defined by the Office for Human Research Protections (OHRP). OHRP considers unanticipated problems involving risks to participants or others to include, in general, any incident, experience, or outcome that meets all of the following criteria:

- Unexpected in terms of nature, severity, or frequency given (a) the research procedures that are described in the protocol-related documents, such as the IRB-approved research protocol and informed consent document; and (b) the characteristics of the participant population being studied;
- Related or possibly related to participation in the research (“possibly related” means there is a reasonable possibility that the incident, experience, or outcome may have been caused by the procedures involved in the research); and
- Suggests that the research places participants or others at a greater risk of harm (including physical, psychological, economic, or social harm) than was previously known or recognized.

8.3.2 UNANTICIPATED PROBLEMS REPORTING

The investigator will report UPs to the reviewing IRB and to the lead PI. The UP report will include the following information:

- Protocol identifying information: protocol title and number, PI's name, and the IRB project number
- A detailed description of the event, incident, experience, or outcome
- An explanation of the basis for determining that the event, incident, experience, or outcome represents an UP
- A description of any changes to the protocol or other corrective actions that have been taken or are proposed in response to the UP

To satisfy the requirement for prompt reporting, UPs will be reported using the following timeline:

- UPs will be reported to the IRB and to the NCI in accordance with policy regarding timeliness of reporting

- All UPs should be reported to appropriate institutional officials (as required by an institution's written reporting procedures), the supporting agency head (or designee), and the OHRP in accordance with policy regarding timeliness

9 STATISTICAL CONSIDERATIONS

9.1 STATISTICAL HYPOTHESES

- Primary Endpoint:

PORT Delay

We hypothesize that, compared with patients who receive usual care, patients who receive NDURE will have a decreased rate of PORT delay (initiation of PORT > 6 weeks after surgery). Alternatively, our null hypothesis is that there will be no difference in the rate of PORT delay between NDURE and usual care.

The preliminary efficacy analysis will be calculated for the primary endpoint over the 6 week time period from the date of definitive surgical resection of the primary tumor.

- Secondary Endpoints:

PORT Delay

We hypothesize that, compared with usual care, NDURE will result in a smaller difference in the rate of PORT delay (initiation of PORT > 6 weeks after surgery) between AA and white patients. Alternatively, our null hypothesis is that there will be no difference in the rate of PORT delay between AA and white patients between NDURE and usual care.

The preliminary efficacy analysis will be calculated for the primary endpoint over the 6 week time period from the date of definitive surgical resection of the primary tumor.

TTP

We hypothesize that, compared with patients who receive usual care, patients who receive NDURE will have a shorter median TTP (time, in days, between the date of definitive surgical resection to the initiation of PORT). Alternatively, our null hypothesis is that there will be no difference in median TTP between NDURE and usual care.

TTP

We hypothesize that, compared with usual care, NDURE will result in a smaller difference in the median TTP between AA and white patients. Alternatively, our null hypothesis is that there will be no difference in the median TTP between AA and white patients between NDURE and usual care.

NDURE Accrual

We hypothesize that at least 60% of eligible subjects for the NDURE study will accrue to the study. Alternatively, our null hypothesis is that less than 60% of eligible subjects for the NDURE study will accrue to the study.

The preliminary feasibility analysis will be calculated for the secondary endpoint using the first 25 patients eligible to accrue to the study, which is expected to occur over 4 months.

NDURE Completion

We hypothesize that at least 85% of subjects who enroll in the NDURE study (at least 13 of 15 subjects) will complete all 3 NDURE sessions. Alternatively, our null hypothesis is that less than 13 of the 15 subjects who enroll in the NDURE study will complete all 3 NDURE sessions.

The preliminary feasibility analysis will be calculated for the secondary endpoint using the first 15 patients who accrue to the study, which is expected to occur over 6 months.

9.2 SAMPLE SIZE DETERMINATION

9.2.1 NDURE FEASIBILITY STUDY

Power and sample size calculations were performed using the University of Iowa Binomial Distribution applet. The sample size justification for this single-arm study is based on the primary feasibility endpoints of NDURE accrual and completion. In the RCT of NDURE, we plan to enroll 60% of eligible patients. We expect similar accrual in this feasibility study. Therefore, we hypothesize that at least 60% of eligible subjects for the NDURE study will accrue to the study. Alternatively, our null hypothesis is that less than 60% of eligible subjects for the NDURE study will accrue to the study. Accruing to NDURE will be considered feasible if at least 15 of 25 eligible subjects enroll. Our sample size for the feasibility study was selected to provide a small probability of having an observed accrual rate of at least 60% when the true accrual probability is actually less than 60%. For example, if the true accrual probability for our proposed design is 45% (35%), the probability of enrolling 15 or more of 25 eligible subjects is only 10% (1%). Additionally, we hypothesize that at least 85% of subjects who enroll in the NDURE study will complete all 3 NDURE sessions. Alternatively, our null hypothesis is that less than 85% of subjects who enroll in the NDURE study will complete all 3 NDURE sessions. That is to say, NDURE will be considered feasible if at least 13 of the 15 subjects enrolled complete all three NDURE sessions. Accordingly, our sample size for the single-arm study was selected to provide a small probability of having an observed completion rate of at least 85% when the true completion probability of the intervention is actually less than 85%. For example, if the true completion probability for our proposed design is 70% (60%), the probability that 13 or more of the 15 enrolled patients complete all three NDURE sessions is 13% (3%). Therefore, the probability of falsely declaring NDURE feasible is reasonably controlled based on this sample size.

9.2.2 RCT OF NDURE VERSUS USUAL CARE

Power and sample size calculations were performed using PASS v08.0.13, “Inequality Tests for Two Independent Proportions.” The primary endpoint for this pilot RCT is the rate of PORT delay, defined as starting PORT > 6 weeks after surgery. Our primary objective is to compare PORT delay rates between the NDURE and usual care arms. We hypothesize that, compared with patients who receive usual care, patients who receive NDURE will have a decreased rate of PORT delay (initiation of PORT > 6 weeks after surgery). Alternatively, our null hypothesis is that there will be no difference in the rate of PORT delay between NDURE and usual care. We assume the rate of PORT delay in the usual care arm will be 45%³³ and target an absolute reduction in PORT delay of 20% (rate of PORT delay in the NDURE arm = 25%)²⁴. This effect size is clinically significant and realistic given results in similar (non-randomized) interventions²⁴. Seventy-five patients in each arm yields 83% power to detect a 20% reduction in PORT delay (45% versus 25%) based on a two-sided Mantel-Haenszel test of two independent proportions assuming a two-sided $\alpha = 0.1$. Our choice of the Mantel-Haenszel test to compare proportions is based on the trial’s stratified design. Our selection of $\alpha = 0.1$ and $1 - \beta = 0.8$ is based on the desire to emphasize power over type I error at this early stage of development (single-site pilot RCT) to ensure follow-up on promising interventions. We therefore consider our RCT to be appropriately and rigorously designed to detect a clinically meaningful reduction in PORT delay. In order to have 150 patients eligible for the

efficacy analysis in the modified ITT population (see **Section 9.3, Population for Analyses**), we plan to enroll 170 patients. Our sample size is inflated by 17% based on historical data. This inflation account for the predictable subset of patients would be enrolled in the study, be randomized to NDURE or Usual Care, receive a portion of the intervention (NDURE Visit 1) and then subsequently develop a study exclusion criterion, namely: 1) failure to undergo curative intent surgery at MUSC (exclusion criteria #4); 2) lack of indication for PORT (with or without chemotherapy) per NCCN Guidelines (exclusion criteria #5). As such, patients who meet study inclusion criteria but subsequently develop exclusion criteria #4 or #5 during the course of the study will be replaced since the primary endpoint is anchored to findings that occur after analysis of the pathologic specimen obtained during surgery.

Every effort will be made to minimize missing data and lost-to-follow-up participants. Participants will complete assessments at baseline and post intervention using an iPad-based REDCap collection method. The program coordinator will attempt to contact patients at least three times using a variety of methods of communication (e.g. text message, phone call, email, mail, etc) to complete outcome measures. This method resulted in 100% instrument completion in prior studies conducted by our team. Patients in the ITT population for whom the primary endpoint is not evaluable due to loss to follow-up will be considered NDURE failures, and their time to PORT will be treated as exceeding 6 weeks for the purposes of analysis (a very conservative approach for this single-arm, pilot RCT).

We note that our accrual rate target of 60%, by which we establish the feasibility of recruitment for this RCT, will have been tested in the feasibility study as described. Refinements to the recruitment strategies and study timeline will occur as needed to ensure that we achieve our accrual targets described below. We propose to accrue 75 patients to each arm (white, n=50 and African American, n=25) to the study over 36 months. Based on data from MUSC/HCC for 2018, it is expected that 125 patients/year will be eligible for the study, of whom 28 (22%) are expected to be African American and 97 (78%) are expected to be white. During the 36-month accrual period, we would expect to screen 375 patients, of whom 83 would be African American and 292 would be white. Based on the PI and study team's prior experience recruiting and enrolling for similar studies embedded into clinical care and the feasibility data gathered from the single-arm pilot of NDURE, we anticipate that 60% of eligible patients will accrue to this study. Based on this 60% accrual rate, over the course of 36 months, we would expect to accrue 225 patients (50 African Americans and 175 white). Thus, by conservative estimates with appropriate over-sampling of African Americans, our overall accrual target (n=150) and for the African American racial subgroup (n=50) appear highly feasible. If continued optimization of enrollment and recruitment strategies fails to yield an accrual rate of 60%, we will extend the duration of the study accrual beyond the planned 36 months by an additional 6 months (and remain within the grant funding period). If we extend the study timeline for accrual by 6 months to 42 months instead of 36 months (and thus screen 437 patients [96 African Americans] instead of 375 [83 African Americans]), we would only need an accrual rate of 52% among African Americans to achieve our racial subgroup distribution of n=50 (and an accrual rate of 29% among white HNSCC patients). For all of the above reasons (PI and team experience, prior feasibility testing, refinement of recruitment protocols, and extension of recruitment period), we are highly confident that we can accrue our overall and racial subgroup targets for the RCT.

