For the RCT comparing NDURE to usual care, we note that our accrual rate target of 60%, by which we establish the feasibility of recruitment for this RCT, will have been tested in the pilot single-arm feasibility study. Refinements to the recruitment strategies and study timeline, as described below, will occur as needed to ensure that we achieve our accrual targets described below. We propose to accrue 75 patients to each arm (white, n=50 and AA, n=25) to the study over 36 months. Based on data from MUSC/HCC for 2018, it is expected that 125 patients/year will be eligible for the study, of whom 28 (22%) are expected to be AA and 97 (78%) are expected to be white. During the 36-month accrual period, we would expect to screen 375 patients, of whom 83 would be AA and 292 would be white. Based on the PI and study team's prior experience recruiting and enrolling for similar studies embedded into clinical care and the feasibility data gathered from the single-arm pilot of NDURE, we anticipate that 60% of eligible patients will accrue to this study. Based on this 60% accrual rate, over the course of 36 months, we would expect to accrue 225 patients (50 AAs and 175 white). Thus, by conservative estimates with appropriate over-sampling of AAs, our overall accrual target (n=150) and for the AA racial subgroup (n=50) appear highly feasible. If continued optimization of enrollment and recruitment strategies fails to yield an accrual rate of 60%, we will extend the duration of the study accrual beyond the planned 36 months by an additional 6 months (and remain within the grant funding period). If we extend the study timeline for accrual by 6 months to 42 months instead of 36 months (and thus screen 437 patients [96

AAs] instead of 375 [83 AAs]), we would only need an accrual rate of 52% among AAs to achieve our racial subgroup distribution of n=50 (and an accrual rate of 29% among white HNSCC patients). For all of the above reasons (PI and team experience, feasibility testing, refinement of recruitment protocols, and extension of recruitment period), we are highly confident that we can accrue our overall and racial subgroup targets for the RCT.

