9.3 POPULATIONS FOR ANALYSES

For the efficacy analysis, we will utilize a modified ITT population. Participants will be part of the modified ITT population as defined by the following criteria:

1. Randomized to NDURE or Usual Care
2. Receipt of curative intent surgery at MUSC
3. Indication for PORT (with or without concurrent chemotherapy) per NCCN Guidelines based on the presence of at least one of the following adverse features on final pathologic evaluation: ENE, positive margin, pT3 or pT4 primary, at least pN1 nodal disease (per AJCC 8th edition for p16-ve

non-oropharyngeal SCC or AJCC 7th edition for p16+ve oropharyngeal SCC), nodal disease in levels IV or V, PNI or LVI

The modified ITT analytic population addresses the fact that eligibility, registration, randomization, and delivery of a portion of the intervention (NDURE or Usual Care) occur prior to definitive treatment of the HNSCC. However, the primary study objective (and endpoint) are defined and evaluable only for patients who undergo surgery for HNSCC and have an indication for adjuvant therapy (which can only be definitively known following surgical resection). Therefore, we expect that a predictable subset of patients will be enrolled in the study, based on meeting all inclusion, be randomized to NDURE or Usual Care, receive a portion of the intervention (NDURE Visit 1) and then subsequently develop a study exclusion criterion based on interval information that becomes available later in the clinical course that cannot be known at the time of study enrollment and registration, namely:

- failure to undergo curative intent surgery at MUSC (exclusion criteria #4)
- lack of indication for PORT (with or without chemotherapy) per NCCN Guidelines (exclusion criteria #5)

As such, patients who meet study inclusion criteria but subsequently develop exclusion criteria #4 or #5 during the course of the study will be replaced since the primary endpoint is anchored to findings that occur after analysis of the pathologic specimen obtained during surgery. Patients in the modified ITT population for whom the primary endpoint is not evaluable due to loss to follow-up will be considered navigation failures, and their time to PORT will be treated as exceeding 6 weeks for the purposes of analysis.

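### The 17% inflation in section 9.2.2 does not turn 150 evaluable patients into 170 enrolled: it gives 176 or 181

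*Combined protocol and SAP*

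**What the plan says.** Section 9.2.2 sizes the RCT at 75 per arm, with 83% power for 45% versus 25% PORT delay at two-sided alpha 0.10. It makes 150 the evaluable number ("In order to have 150 patients eligible for the" efficacy analysis in the modified ITT population) and continues: "we plan to enroll 170 patients. Our sample size is inflated by 17% based on historical data". The inflation is for patients who are randomised, start the intervention, and then either do not have curative surgery at the site (exclusion criterion 4) or have no pathological indication for PORT (criterion 5). Patients who "subsequently develop exclusion criteria #4 or #5 during the course of the study will be replaced"; sections 7.2 and 9.3 also provide for replacement.

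The accrual text, in 9.2.2 and almost identically in 5.5, works from other numbers. "Based on data from MUSC/HCC for 2018, it is expected that 125 patients/year will be eligible for the study", and then "During the 36-month accrual period, we would expect to screen 375 patients", which is 3 × 125. Of the 375, 83 are expected to be African American (AA). At 60% accrual it expects 225 enrolled, 50 of them AA, and concludes that "our overall accrual target (n=150) and for the African American racial subgroup (n=50) appear highly feasible". For an extension to 42 months, with 96 AA patients screened, 5.5 says "we would only need an accrual rate of 52% among AAs to achieve our racial subgroup distribution of n=50". Neither the 170 nor the 17% appears in this accrual text.

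**The concern.** A sample-size statement should be reproducible from its own inputs, and this one is not. The 17% is the only figure the protocol gives for loss to exclusion criteria 4 and 5 after randomisation, and that loss is the reason for having a modified ITT population. As printed, a reader cannot tell whether the trial was planned for a loss of about 12%, 14.5% or 17%, and so cannot judge later whether exclusions are running above plan. The enrolment total is also in doubt by 6 to 11 patients.

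A lesser question follows. The accrual text measures itself against 150 and 50 AA, which 9.2.2 has just treated as numbers left after this loss. Whether that matters depends on what the 125 per year counts.

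**Working it through.** **Inputs, all from 9.2.2.** Evaluable target 150 (75 per arm); planned enrolment 170; inflation 17%; delay rates 45% and 25%; two-sided alpha 0.10. Accrual: 83 AA patients over 36 months, 96 over 42 months, 60% accrual, 225 expected overall.

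**Reproducing the plan's power.** Two-proportion test with pooled variance under the null, n per arm, mean rate 0.35:

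power = Φ{[0.20 − 1.645 × √(2 × 0.35 × 0.65/n)] / √[(0.45 × 0.55 + 0.25 × 0.75)/n]}

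With n = 75: (0.20 − 1.645 × 0.0779)/0.0762 = 0.944, so power is 82.7%. This matches the stated 83%, so the base of 150 is sound.

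**The inflation.**
- As a multiplier: 150 × 1.17 = 175.5, so 176.
- As a loss rate: 150/(1 − 0.17) = 180.7, so 181.
- What 170 implies: 170/150 = 1.133, an inflation of 13.3%; 20/170 = 11.8%, the loss it covers.
- A 17% multiplier corresponds to a loss of 1 − 1/1.17 = 14.5%.

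Neither reading gives 170. Two other bases come close (145 × 1.17 = 169.7 and 140/0.83 = 168.7), but the text fixes the base at 150.

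**If enrolment stopped at 170 with no further replacement.**
- 17% as a loss rate: 170 × 0.83 = 141 evaluable, power 80.6%.
- 17% as a multiplier: 170/1.17 = 145 evaluable, power 81.6%.

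**Room in overall accrual.** 225 expected exceeds 181. If the 125 per year is counted before the loss, 225 × 0.83 = 187 evaluable, still above 150.

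**AA accrual.** At 36 months, 83 × 0.60 = 49.8 against 50. At 42 months, 96 × 0.60 = 57.6. If the 125 is counted after the exclusions, the stated 52% stands (50/96 = 52.1%).

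If the 125 is counted before the exclusions, and if AA loss equals overall loss (both assumptions; loss 11.8% to 17%), the AA enrolment needed for 50 evaluable is:
- 11.8% loss: 50 × 170/150 = 56.7, so 57. That is 57/83 = 68.7% over 36 months or 57/96 = 59.4% over 42 months.
- 14.5% loss: 50 × 1.17 = 58.5, so 59. That is 71.1% or 61.5%.
- 17% loss: 50/0.83 = 60.2, so 61. That is 61/83 = 73.5% or 61/96 = 63.5%.

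**The case against.** The strongest reply is that this is a one-figure slip with no consequence. The analysed number is governed by replacement up to 150, nothing calls 170 a ceiling, and expected accrual leaves ample room overall. That stands as to consequence. It does not make the figures agree: if the loss really is 17%, replacement up to 150 takes enrolment past the printed 170.

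A reader might infer that the trial is underpowered. The documents do not support that. A drop to 141 evaluable requires stopping at 170 without replacing anyone, which is not planned, and even then power stays above the plan's own 80%.

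A reader might also infer that the AA target will be missed, or that the 52% fallback is wrong. That is not established either. Criteria 4 and 5 are listed among the formal exclusions in 5.2, so the word eligible may already be net of them, and then there is no AA shortfall from this loss. Against that reading, the same 125 per year is used as the number screened, and 9.3 says these exclusions rest on "interval information that becomes available later in the clinical course that cannot be known at the time of study enrollment and registration". The documents leave the matter open. The lack of AA margin is also confined to 36 months: at 42 months, 60% accrual gives 57.6 enrolled against 50, although the extension is written for accrual below 60% and not for this loss.

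**Conclusion.** The mismatch is certain and needs no assumption: 150, 170 and 17% cannot all be right. The printed enrolment is 6 below 176 and 11 below 181, or else the 17% should read about 13% (as an inflation) or 12% (as a loss). Nothing elsewhere in the document repairs it. The effect on the primary comparison is small: none if replacement runs to 150, and at worst about 81% power instead of 83% at two-sided alpha 0.10.

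The AA part is a request for clarification and not a demonstrated error. It becomes a matter of substance only if the 125 per year is counted before exclusions 4 and 5 and AA loss equals overall loss. On those two assumptions, about 69–73% accrual over 36 months or 59–64% over 42 months would be needed for 50 evaluable AA patients.

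**What to change.** In 9.2.2, give the historical loss and the formula, and make the three figures agree in one of two ways:
- keep 170 and say that it allows for about 12% exclusion after randomisation; or
- if the historical loss is 17%, say that replacement up to 150 implies about 181 enrolled (176 if 17% is meant as a multiplier).

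In 5.5 and 9.2.2, add a sentence saying whether the 125 per year is counted before or after exclusion criteria 4 and 5. Only if before, restate the AA enrolment target as 57–61, with the accrual rates needed over 36 and 42 months and the assumption about AA loss.

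The cost is one corrected figure and one sentence. If the loss is 17%, stated enrolment rises by 6 or 11 patients, within the 225 expected overall. If the 125 is counted before the exclusions, the stated AA accrual outlook becomes less favourable. The design, the target of 25 AA patients per arm and the replacement rule can stay as they are.
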